### **3. Study Design**

We will conduct 10 intervention groups and 10 standard of care control groups of about 15 participants each (n=300). After participants complete the baseline assessment, we will randomize them into the intervention or standard of care control groups. Participants will complete audio computer-assisted interviews at baseline, and 4, 8, and 12-month follow-ups. The intervention will last 8 weeks (7 sessions of content plus a "graduation").

The proposed study is a partnership among academic researchers and stakeholders of Los Angeles County (LAC) Latinx and HIV-affected communities. Bienestar will be a full and equal partner throughout the research. Bienestar, LAC's largest Latinx-serving HIV service organization, provides services (e.g., case management, substance use, mental health) in 7 offices in LAC to people living with HIV and HIV prevention to those at risk.

Participants in the standard of care control group will be provided with information about an ongoing weekly two-hour open wellness-oriented support group available to all clients at Bienestar. The program includes an open support group; psychoeducation on wellness topics (e.g., HIV prevention, sexuality, spirituality, self-esteem, other health promotion topics); and social and cultural activities with food, art, and music.

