## 5. Statistical Analysis

**Main Analyses.** We hypothesize that the coping intervention will result in higher likelihoods of regular HIV testing and PrEP use, and improved coping with stigma (e.g., reduced internalized stigma). We will perform descriptive statistics and transform outcomes with skewed distributions (log or other as appropriate) to stabilize error variances and reduce outlier influence in regressions. We will select covariates from variables hypothesized on the basis of theory and previous research to predict outcomes, and for which we find support in bivariate baseline analyses (at  $p < .10$ ). We will use intention-to-treat analysis, i.e., analyze participants according to the group to which they were randomized, regardless of session attendance. Aim 1. We will use repeated-measures logistic regression for our primary HIV testing and PrEP dichotomous outcomes. Aim 2. For secondary outcomes (e.g., coping, internalize stigma) on which the coping intervention shows significant effects, to test mediation we will compare: (a) Aim 1 models, adding baseline measures of hypothesized mediators; and (b) the same models as in (a), adding post-intervention measures of hypothesized mediators. We will examine whether including post-intervention mediators in (b) decreases the coefficient for intervention effects on the outcome relative to the corresponding coefficient from (a). We will test interactions between each moderator and intervention group in the models for Aim 1.

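### Aim 2 reads mediation from a fall in a logistic coefficient; in a marginal model that fall understates the mediated share, and the plan leaves the model form open

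*Combined protocol and SAP*

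**What the plan says.** Section 5, Aim 1, sets the outcome model: "We will use repeated-measures logistic regression for our primary HIV testing and PrEP dichotomous outcomes". It does not say whether this is a marginal (GEE) or a random-effects model.

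Aim 2 then compares two nested versions of that model. The first is "a) Aim 1 models, adding baseline measures of hypothesized mediators". The second is "b) the same models as in (a), adding post-intervention measures of hypothesized mediators". Mediation is read from whether "including post-intervention mediators in (b) decreases the coefficient for intervention effects on the outcome relative to the corresponding coefficient from (a").

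The comparison is made only for secondary outcomes "on which the coping intervention shows significant effects, to test mediation we will compare". The expected direction is that "the coping intervention will result in higher likelihoods of regular HIV testing and PrEP use, and improved coping with stigma", so direct and indirect effects are expected to share a sign.

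Section 5 gives no common scale for the two coefficients, no indirect-effect estimate, and no test or interval for the fall. It does not say which follow-up wave supplies the post-intervention mediator.

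**The concern.** In a linear model, the fall in the treatment coefficient when a mediator is added equals the indirect effect. In a logistic model it need not. Adding a variable that predicts the outcome raises the other log odds ratios in absolute size, even if treatment does not move that variable. The change from (a) to (b) can therefore be mediation minus a rescaling term of opposite sign. Having baseline mediators in both models does not remove this, because the post-intervention measure still adds prognostic information.

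Explaining how the intervention works is the second objective in section 2, and this comparison is the only mediation method described. If the rescaling applies, the fall is too small, and the loss grows with the strength of the mediator's link to the outcome. The strongest mechanisms would be understated most. More participants would not cure it.

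**Working it through.** The documents give no mediation figure to reproduce. They give the model type, the (a)/(b) contrast and the significance condition (section 5). Section 3 gives the size: "We will conduct 10 intervention groups and 10 standard of care control groups of about 15 participants each (n=300"), about 150 per arm. It also gives three follow-up waves: "Participants will complete audio computer-assisted interviews at baseline, and 4, 8, and 12-month follow-ups". All effect sizes below are assumptions.

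**Set-up.** T is the arm (1:1). M0, the baseline mediator, has SD 1. The post-intervention mediator is M1 = aT + 0.6·M0 + e, with SD(e) = √(1 − 0.36) = 0.8. The outcome follows logit P(Y) = −0.8 + cT + b·M1 + u, where u is person-level heterogeneity. The control event rate is about one third. There is no unmeasured mediator–outcome confounding.

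- True mediated share: ab/(c + ab).
- Apparent share: [coef(a) − coef(b)] / coef(a).

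**Main example, marginal fit, no heterogeneity: a = 0.25, b = 1 (odds ratio 2.7 per SD), c = 0.6.**

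- True share: 0.25/0.85 = 29.4% (30.3% on the probability scale).
- Large-sample coefficients: 0.751 in (a) and 0.600 in (b). Fall 0.151; apparent share 0.151/0.751 = 20.1%.
- Where the rest goes: with e held fixed, the total effect is 0.85. Model (a) averages over e and returns 0.751, a loss of 0.85 − 0.751 = 0.099. The fall is 0.250 − 0.099 = 0.151.

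**Marginal fit, other values.**

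| a, b, c | True share | Apparent, u = 0 | Apparent, SD(u) = 1.5 |
|---|---|---|---|
| 0.25, 0.4, 0.6 (OR 1.5 per SD) | 14% | 12% | 13% |
| 0.25, 1, 0.6 (OR 2.7 per SD) | 29% | 20% | 24% |
| 0.1, 1, 0.7 | 12.5% | 1% | 6% |
| 0, 1, 0.6 | 0% | coefficient rises 13% | coefficient rises 7% |

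**Ranking.** A second grid used a 0.5 baseline-to-post correlation, intercept −0.85, a = 0.3 and c = 0.7. For b = 1.2, 1.6 and 2.0 the product ab is 0.360, 0.480 and 0.600 (true shares 34%, 41% and 46%). The marginal falls without heterogeneity are 0.174, 0.177 and 0.170, so three different mediators look alike. With SD(u) = 1.5 the falls are 0.177, 0.204 and 0.219, against products of 0.261, 0.351 and 0.442 on the model (b) scale. The order is kept but the differences are compressed. These are strong mediators. At b = 0.5 the fall is 0.115 against 0.150 (77% captured) without heterogeneity, and 87% is captured with it.

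**Random-intercept fit, time-fixed mediator (a = 0.3, c = 0.7, n = 20,000).** The falls are 0.149, 0.349 and 0.503 against products of 0.150, 0.360 and 0.480 for b = 0.5, 1.2 and 1.6. There is no systematic shortfall, because the added mediator lowers the random-effect SD (1.86 to 1.53 at b = 1.2) instead of rescaling the coefficient. In the main example (n = 12,000) a time-fixed mediator gave a drop of 31.6%, and a mediator measured at each wave gave 24.6%, against a true 29.4%.

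**Effect of the significance condition at n = 300.** Ignoring group clustering, SE = 0.8·√(2/150) = 0.092.

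- Shift of 0.25: 0.25/0.092 = 2.71, so the condition is met with probability Φ(2.71 − 1.96) ≈ 0.77.
- Shift of 0.1: 0.1/0.092 = 1.08, giving Φ(1.08 − 1.96) ≈ 0.19.

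A simulation with 2,000 replicates, three waves, a pooled logistic fit and a time-fixed mediator covered six scenarios. In the a = 0.1 case, 49% of all trials showed no fall. Among trials that met the condition, none lacked a fall in any scenario.

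**The case against.** Four points can be made for the plan.

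1. **The criterion is directional.** The plan asks whether the coefficient decreases and defines no percentage mediated. In the main example it still decreases, so the yes/no answer is right. This stands. But with no interval or threshold, the size of the decrease is what readers will use to judge and compare mechanisms, and the size is what is distorted.

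2. **The significance condition screens out the worst cases.** A reader might infer from the 12.5%-to-1% example that real mediation would be hidden. The plan does not support that reading: so small a shift would seldom qualify, and among qualifying simulated trials the coefficient always fell. That check ignored clustering, used the same mediator measure for the condition and the model, and did not cover every parameter value.

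3. **The model form is open.** A reader might also infer that the comparison fails under any repeated-measures logistic model. It does not. With a random intercept and one post-intervention mediator value the shortfall is nearly absent, and section 4 places the 4-month survey soon after the sessions end, so a single value is plausible. This stands as a limit on the point. The plan as written equally permits a marginal model, or a mediator taken at every wave.

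4. **A weak mediator loses little, and with no direct effect the share is correct (100%).** Both are true. However, the analysis cannot presume either case in advance.

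**Conclusion.** The point holds conditionally. If the Aim 1 model is marginal and direct and indirect effects share a sign, the (a)-to-(b) fall understates the mediated share: 14% appears as about 12% at an odds ratio of 1.5 per SD, and 29% as 20 to 24% at 2.7 per SD. With a random intercept and a time-fixed mediator there is essentially no understatement. With a mediator measured at each wave a smaller one may remain (29% as 25% in one fit).

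The likely harm is a wrong size and a flattened ranking of mechanisms in a secondary aim, not a missed mediator. The documents do not support a claim that mediation would be masked altogether. The direction follows from non-collapsibility. The sizes rest on the assumed mediator shift, mediator–outcome link, event rate and heterogeneity, none of which the documents give.

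**What to change.** In section 5, Aim 2:

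- State whether the repeated-measures logistic model is marginal or random-intercept, and which wave supplies the post-intervention mediator.
- Replace the coefficient comparison with indirect and direct effects on the probability scale. Fit model (b) together with a model for the mediator given arm and baseline mediator, then standardize over the sample. Report the difference in the probability of regular testing, and of PrEP use, that runs through the mediator and the part that does not, each with a confidence interval.
- If a coefficient comparison is kept, use the Karlson–Holm–Breen version: put into model (a) the residual of the post-intervention mediator after regression on arm and baseline mediator. Both models then share one scale. In the main example, coefficient (a) becomes 0.6 + 0.25 = 0.85, the fall is 0.25 and the share is 0.25/0.85 = 29.4%.

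The cost is SAP wording, standard code and a little more analysis work. No new data are needed. The probability-scale effects still assume no unmeasured mediator–outcome confounding, as does the present comparison; the SAP should say so.

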### **2. Objectives**

This objectives of this study are to: 1) conduct a randomized controlled trial of a coping intervention that is a culturally congruent CBT group intervention for immigrant LSMM, to test intervention effects on regular HIV testing and PrEP use; 2) examine mechanisms of intervention effects on regular HIV testing and PrEP use, including more effective coping; and 3) conduct a cost-effectiveness analysis of the intervention.

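### Aim 2 sets out to test mediation but, beyond a gate on the intervention-to-mediator effect, asks only whether the intervention coefficient falls

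*Combined protocol and SAP*

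**What the plan says.** Section 2 (Objectives) makes mechanisms the second of three objectives: to "examine mechanisms of intervention effects on regular HIV testing and PrEP use, including more effective coping".

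The only text on how this will be analysed is the Aim 2 part of Section 5 (Statistical Analysis). It has three elements:

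- **A gate.** Mediation is looked at only for secondary outcomes "on which the coping intervention shows significant effects". No significance level is attached to this.
- **Two models.** Model (a) is the Aim 1 repeated-measures logistic regression plus the baseline mediators. Model (b) is "the same models as in (a), adding post-intervention measures of hypothesized mediators".
- **A criterion.** The analysts look at whether the addition "decreases the coefficient for intervention effects on the outcome relative to the corresponding coefficient from (a").

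The direction expected of the mediators is also stated: "improved coping with stigma (e.g., reduced internalized stigma"). No standard error, interval or minimum size is given for the change in the coefficient. Nothing says that the mediator's own coefficient in model (b) will be tested. The only numerical p-value threshold in the section, .10, is for covariate selection.

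**The concern.** Mediation needs two links: the intervention must move the mediator, and the mediator must affect the outcome. The gate tests the first. The second is left to the direction in which the intervention coefficient moves between two fitted models, and that estimate will move one way or the other by chance even when the second link is absent.

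The case that matters is a realistic one. A coping programme may well improve coping or reduce internalized stigma without either having any bearing on HIV testing or PrEP use. Read literally, the criterion could then label a bystander variable as a mechanism, under one of the trial's three objectives.

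**Working it through.** **Inputs from the documents.** Section 3 (Study Design) gives (10 + 10) groups × 15 = 300 participants, which agrees with the stated n=300. It also gives three post-baseline waves: "Participants will complete audio computer-assisted interviews at baseline, and 4, 8, and 12-month follow-ups". The documents state no significance level, path size, power or mediation figure, so there is no figure of the plan's own to reproduce.

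**Why a fall alone says little.** Write *a* for the intervention's effect on the mediator and *b* for the mediator's coefficient in model (b). In a linear model the change is exactly

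coefficient in (a) − coefficient in (b) = estimated *a* × estimated *b*,

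and in a logistic model this holds approximately. Once the gate is passed in the expected direction, estimated *a* is positive, so the sign of the change is the sign of estimated *b*. If true *b* = 0, that estimate is about equally likely to be positive or negative, and the coefficient falls in about half of trials.

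**Simulation assumptions (not in the documents).** There were 4,000 trials per scenario, with:
- 150 per arm, three waves, and one mediator measured once after the intervention, correlated 0.5 with baseline;
- logit intercept −0.8, person random effect SD 1 or 2, no group clustering;
- models (a) and (b) fitted as pooled logistic regressions with person-clustered standard errors;
- gate at two-sided p<0.05 in the hypothesised direction, from a baseline-adjusted linear regression.

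The gate can be checked by hand. The standard error is 2 × √(1 − 0.5²) / √300 = 0.10. Shifts of 0.25 and 0.4 SD therefore give z of about 2.5 and 4, consistent with the simulated pass rates of about 70% and 98%.

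**Null case 1: the intervention moves the mediator, but the mediator has no outcome effect.** Shift 0.25 or 0.4 SD; direct log-odds effect 0.3, 0.5 or 0.8; person SD 1 or 2 (12 scenarios). Among gated trials:

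| Rule | Rate |
|---|---|
| Any fall in the coefficient | 49% to 52% |
| Fall above 10%, direct effect 0.3 | 21% to 33% |
| Fall above 10%, direct effect 0.5 | 10% to 26% |
| Fall above 10%, direct effect 0.8 | 2% to 14% |
| Both paths significant, either direction | 4.8% to 5.7% |
| Both paths significant, hypothesised direction | 2.1% to 3.0% |
| 95% interval for the product of paths excludes zero | 3.9% to 5.6% |

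As a share of all trials, gate plus any fall is about 0.70 × 0.50 = 35% at the 0.25 SD shift and 0.98 × 0.50 = 49% at 0.4 SD. For the joint test it is about 0.70 × 0.05 = 3.5% and 0.98 × 0.05 = 4.9%.

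**Null case 2: the intervention does not move the mediator.** With *b* = 0 or 0.5, gate plus any fall occurs in 1.0% to 2.6% of all trials. Without clustering, the gate does its job here.

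**Sensitivity.** A separate simulation used one wave, shifts of 0.3 and 0.5 SD, direct effects from 0 to 0.8, a 20% loss scenario (n=240) and a lower-prevalence scenario. Any fall occurred in 49% to 51% of gated null trials, and the added mediator-outcome test flagged 4.5% to 5.5%.

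**The case against.** - **The plan says it will *examine* the change, and the source is a protocol summary.** It does not promise to claim mediation for every fall, and it states no significance level for Aim 1 either. That stands, and it is why the 49% to 52% is not an error rate for this trial. But the same sentence announces a test of mediation, and no rule says when mediation would be judged absent.
- **The one-half figure is only symmetry.** True, and that is the point: it hardly depends on the assumed effect sizes. If objective 2 is read as presupposing an Aim 1 effect, restricting to gated trials with a significant Aim 1 effect leaves the rate of any fall at 45% to 53%.
- **The 10% threshold is not in the plan.** Correct. It shows only that an informal cut-off depends on the unknown direct effect. Counting only trials with a positive model (a) coefficient gives 17% to 24%, 8% to 22% and 1% to 13% at direct effects 0.3, 0.5 and 0.8; restricting to significant Aim 1 effects gives 11% to 13%, 4% to 12% and 1% to 9%.
- **Participants are treated in groups, and the simulation ignores this.** With an assumed intraclass correlation of 0.05, an unmoved mediator, *b* = 0.5 and person SD 1, gate plus fall rises from about 2.5% to 5.0% (intervention arm clustered) or 8.2% (both arms). The joint test gives the same 5.0% and 8.2%. The remark that the gate works, and the operating figures for the fix, are therefore best case. Clustering does not rescue the criterion in null case 1.
- **The plan does not pair mediator waves with outcome waves, or say whether several mediators enter together.** This also stands. A significant mediator coefficient at the same wave could reflect reverse ordering. The plan's own comparison shares the weakness.

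**Conclusion.** The concern holds. Past the gate, the stated comparison cannot separate a mediator from a variable that the intervention moves but that does nothing to the outcome: the coefficient falls in about half of such trials, against about 5% if the mediator-outcome path is also tested. The one-half figure follows from the structure of the comparison and is secure. The 10% figures, and the power figures below, depend on assumed path sizes, person-level variation and no group clustering. The omission itself is certain, since no other section adds a rule.

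This is worth correcting before analysis because it leaves a stated objective without a decision rule. It is a risk left open by the wording, not a demonstrated error, and it does not touch the Aim 1 analysis.

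**What to change.** State in Section 5 that mediation will be claimed only if a 95% confidence interval for the indirect effect excludes zero. A simpler alternative is to require both the intervention-to-mediator effect and the mediator coefficient in model (b) to be significant in the hypothesised direction, adjusting for the baseline mediator as both models already do. If neither is wanted, say that the coefficient change is descriptive only. Also state the assumption of no unmeasured mediator-outcome confounding, which none of these options repairs, and say which mediator wave goes with which outcome wave.

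The cost is one or two sentences and little programming, with no new data, because model (b) already estimates the mediator coefficient. The downside is that fewer real mediators are claimed. Simulated detection rates (share of all trials, direct effect 0.4; each cell gives mediator shifts of 0.25 / 0.4 SD):

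| Mediator log-odds per SD | Person SD | Gate plus any fall, all visits | Joint test, all visits | Joint test, 80% of visits |
|---|---|---|---|---|
| 0.3 | 1 | 70% / 98% | 54% / 76% | 49% / 69% |
| 0.3 | 2 | 68% / 93% | 29% / 41% | 27% / 35% |
| 0.5 | 1 | 70% / 98% | 69% / 97% | 69% / 96% |
| 0.5 | 2 | 69% / 97% | 57% / 80% | 54% / 74% |

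The indirect-effect interval is 0 to 3 points below the joint test throughout. The loss ranges from 1 point (70% − 69%) to 52 points (93% − 41%) with all visits observed, and is largest for a weak mediator with large person-level variation. The higher rates for gate plus any fall come from a rule that also passes about half of gated bystander variables, so they are not power at a comparable error rate.
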